9.3.1 Definition of AE

AE Definition

An AE is any untoward medical occurrence in a clinical study participant, temporally associated with the use of study intervention, whether or not considered related to the study intervention.

NOTE: An AE can therefore be any unfavorable and unintended sign (including an abnormal laboratory finding), symptom, or disease (new or exacerbated) temporally associated with the use of study intervention.

Events Meeting the AE Definition

- Any abnormal laboratory test results or other safety assessments, including those that worsen from baseline, considered clinically significant in the medical and scientific judgment of the investigator.
- Exacerbation of a chronic or intermittent pre-existing condition including either an increase in frequency and/or intensity of the condition.
- New conditions detected or diagnosed after study intervention even though it may have been present before the start of the study.
- Signs, symptoms, or the clinical sequelae of a suspected overdose of either TNFi or a concomitant medication. Intentional overdose taken with possible suicidal/self-harming intent should be reported regardless of sequelae.
- The signs, symptoms, and/or clinical sequelae resulting from lack of efficacy will be reported as AE or SAE if they fulfil the definition of an AE or SAE.

Events NOT Meeting the AE Definition

- Any clinically significant abnormal laboratory findings or other abnormal safety assessments which are associated with the underlying disease, unless judged by the investigator to be more severe than expected for the participant's condition.
- The disease/disorder being studied or expected progression, signs, or symptoms of the disease/disorder being studied, unless more severe than expected for the participant's condition.
- Medical or surgical procedure: the condition that leads to the procedure is the AE.
- Situations in which an untoward medical occurrence did not occur (social and/or convenience admission to a hospital).
- Anticipated day-to-day fluctuations of pre-existing disease(s) or condition(s) present or detected at the start of the study that do not worsen.

9.3.2 Definition of SAE

An SAE is defined as any serious adverse event that, at any dose:

a. Results in death

b. Is life-threatening

The term 'life-threatening' in the definition of 'serious' refers to an event in which the participant was at risk of death at the time of the event. It does not refer to an event, which hypothetically might have caused death, if it were more severe.

c. Requires inpatient hospitalization or prolongation of existing hospitalization

In general, hospitalization signifies that the participant has been admitted (usually involving at least an overnight stay) at the hospital or emergency ward for observation and/or treatment that would not have been appropriate in the physician's office or outpatient setting. Complications that occur during hospitalization are AEs. If a complication prolongs hospitalization or fulfills any other serious criteria, the event is serious. When in doubt as to whether "hospitalization" occurred or was necessary, the AE should be considered serious. Hospitalization for elective treatment of a pre-existing condition that did not worsen from baseline is not considered an AE.

d. Results in persistent or significant disability/incapacity

The term disability means a substantial disruption of a person's ability to conduct normal life functions. This definition is not intended to include experiences of relatively minor medical significance such as uncomplicated headache, nausea, vomiting, diarrhea, influenza, and accidental trauma (e.g., sprained ankle) which may interfere with or prevent everyday life functions but do not constitute a substantial disruption.

e. Is a congenital anomaly/birth defect

f. Other situations:

Medical or scientific judgment should be exercised by the investigator in deciding whether SAE reporting is appropriate in other situations such as significant medical events that may jeopardize the participant or may require medical or surgical intervention to prevent one of the other outcomes listed in the above definition. These events should usually be considered serious.

9.3.3 Recording and Follow-Up of AE and/or SAE

AE and SAE Recording

- When an AE/SAE occurs, it is the responsibility of the investigator to review all documentation related to the event and record all relevant AE/SAE information.
- The investigator will attempt to establish a diagnosis based on signs, symptoms, and/or other clinical information, and whenever possible, this diagnosis will be documented as the AE/SAE.

Assessment of Intensity

The investigator will assess the intensity for each AE/SAE according to the following categories:

- Mild:** An event that is easily tolerated by the participant, causing minimal discomfort and not interfering with everyday activities.
- Moderate:** An event that causes sufficient discomfort to interfere with normal everyday activities.
- Severe:** An event that prevents normal everyday activities. An AE that is assessed as severe should not be confused with an SAE. Severe is a category utilized for rating the intensity of an event; and both AEs and SAEs can be assessed as severe.

Assessment of Causality

- The investigator is obligated to assess the relationship between study intervention and each occurrence of each AE/SAE and must document this review in the medical notes.
- A “reasonable possibility” of a relationship conveys that there are facts, evidence, and/or arguments to suggest a causal relationship, rather than it not being ruled out. Clinical judgment and the Product Information is applied to determine the relationship. Alternative causes (e.g. underlying disease, concomitant therapy, other risk factors) and temporal relationship of the event to study intervention will be considered and investigated.

Follow-up of AEs and SAEs

- The investigator is obligated to perform or arrange for any supplemental evaluations as medically indicated to elucidate the nature and/or causality of the AE or SAE as fully as possible.
- New or updated information will be recorded in the originally submitted documents.

9.4 Appendix 5: ASAS Classification criteria for Axial Spondyloarthritis

In patients with ≥ 3 months history of back pain and age of onset <45 years	

Sacroiliitis on imaging* and ≥ 1 SpA feature
 
OR
 
HLA B27 and ≥ 2 SpA features
	
SpA- features
 
 • Inflammatory back pain • Arthritis • Enthesitis (heel) • Uveitis • Dactylitis • Psoriasis • Inflammatory bowel disease • Good response to NSAIDs • Family history of SpA • HLA B27 • Elevated CRP

Sacroiliitis on imaging
 
 • Active (acute) inflammation on MRI highly suggestive of sacroiliitis associated with SpA • Definite radiographic sacroiliitis according to the modified New York criteria 	

9.5 Appendix 6: Patient-reported outcomes

9.5.1 Patient global assessment

Vi ber deg vennligst vurdere aktiviteten i din revmatiske sykdom i løpet av den siste uken.

Når du tar alle symptomer med i betrakting, hvordan synes du tilstanden er? *

[figure not shown]
Angi på en skala fra 0 (Bra, ingen symptomer) til 10 (Svært dårlig)

9.5.2 Pain assessment

Hvor mye smerte har du hatt i løpet av den siste uken? *

Angi på en skala fra 0 (Ingen smerter) til 10 (Uutholdelige smerter)

9.5.3 Joint pain assessment

Hvordan vil du beskrive de leddsmertene du vanligvis har hatt den siste uken? *

Angi på en skala fra 0 (Ingen smerter) til 10 (Uutholdelige smerter)

9.5.4 Patient reported flare

Har du sykdomsoppbluss (klar forverring) av din revmatiske sykdom nå?

- Nei
- Ja
- Usikker

Hvis du svarte «Ja» eller «usikker», hvilken dato startet forverringen? _____._____.20____

Omtrent hvor mange dager varte forverringen/har forverringen vart? _____ dager

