2.3.4 Objectives and endpoints

Objectives	Endpoints
Primary	
Assess if two, new follow-up strategies are non-inferior compared to conventional follow-up with hospital visits in terms of maintaining low disease activity	Disease activity (ASDAS) at 6, 12 and 18 months
Secondary	
Compare additional measures of clinical efficacy between the treatment arms	Efficacy measures outlined in section 7.2 at each time point
Compare the safety of the two, new follow-up strategies in axSpA with the conventional follow-up strategy	Safety profile and adverse events throughout the study + doses of analgesics + prescribed antibiotics
Assess if the patients and HPs are equally adept to judge the need for consultation	Comparing the proportions that are scheduled for a visit when a serious disease activity worsening (flare) occurs
Additional	
Evaluate cost effectiveness of remote monitoring in axSpA	Health related quality of living, health care utilization and costs related to the societal perspective (e.g. work participation) as outlined in section 7.4. at each, or a combination, of time points.
Examine fluctuations in disease activity and physical activity level over time	Self-reported disease activity every month, blood tests every 6 th month, and monthly CRP for a subgroup of participants. Physical activity data from wearing an activity tracker in the two, new follow-up strategy arms
Examine if flares can be detected based on changes in monitored physical activity level	Physical activity tracker data (steps per day and minutes with moderate and high intensity activity levels) and measures of disease activity
Investigate barriers and facilitators for remote monitoring among HPs and patients	Questionnaire at baseline among HPs and patients
Investigate the HPs' and patients' perspectives and satisfaction with remote monitoring	Semi-structured interviews of 10-15 patients and their treating rheumatologist and/or nurse
Investigate HPs' and patients' experiences with video consultations, as compared to hospital visits and telephone consultations, and the impact of self-reporting on the follow-up care	Semi-structured interviews and observations of 10-15 patients and their treating rheumatologist and/or nurse

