7.2 Efficacy assessments

7.2.1 Patient-reported outcome measures

At Baseline (after screening, but before the randomization), patient demographics and PROs be collected using a digital device at the hospital.

Every 6. month, patients will receive a link a digital survey ("Nettskjema" (Services for sensitive data (TSD), University of Oslo)). Collection of a few PROs from patients will be done monthly for the Remote monitoring arm and every third month for the Patient-initiated care arm using the MyDignio app. The participants in these two intervention arm will also report blood test results every 6. month using the MyDignio app.

- **Patient global assessment of disease activity** (PGA) (Visual Analogue Scale, NRS 0-10) (All arms: Baseline, 6-, 12- and 18-months) (Remote monitoring arm: each month) (Patient-initiated care arm: each 3rd month)
- **Patient-reported flares** (All arms: 6-, 12- and 18-months) (Remote monitoring arm: each month) (Patient-initiated care arm: each 3rd month)
If the patient responds "yes" or "uncertain" to the question if they have experienced a significant worsening of symptoms (reflecting a flare in disease activity), they will be asked which date the flare occurred and the number of days it lasted.
- **Bath Ankylosing Spondylitis Disease Activity Index** (BASDAI) (All arms: Baseline, 6-, 12- and 18-months) (Remote monitoring arm: each month if disease worsening) (Patient-initiated care arm: each 3rd month if disease worsening)
BASDAI is a 6 item questionnaire (NRS 0-10) used to assess disease activity in ankylosing spondylitis³⁴. The score is the sum (of the first four individual questions and the mean of questions five and six) divided by five.
- **Bath Ankylosing Spondylitis Functional Index** (BASFI) (Baseline)
BASFI is a 10 item questionnaire (NRS 0-10) used to assess disease activity in ankylosing spondylitis³⁴. The score is the sum of each individual question divided by 10.
- **Patient-reported pain (general)** Single item (NRS 0-10) (Baseline, 6-, 12- and 18-months)

- **Patient-reported joint pain** Single item (NRS 0-10) (Baseline, 6-, 12- and 18-months)
- **Patient-reported global change in disease activity.** Single item with seven-point response scale ranging from "Much worse" to "Much better" (6-, 12- and 18-months)
- **Patient-reported global change in activity impairment.** Single item with seven-point response scale ranging from "Much worse" to "Much better" (6-, 12- and 18-months)

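### The flare form asks only about a flare present now, while section 7.2.1 describes flares the patient has experienced, so a flare that ends between forms without a visit has no stated route to be recorded on this item

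*Protocol*

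**What the plan says.** Protocol section 7.2.1 lists patient-reported flares among the efficacy measures and refers to "the question if they have experienced a significant worsening of symptoms (reflecting a flare in disease activity"). A patient who answers yes or uncertain is then asked "which date the flare occurred and the number of days it lasted". No recall window is stated. The schedule is "All arms: 6-, 12- and 18-months) (Remote monitoring arm: each month) (Patient-initiated care arm: each 3rd month".

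The form itself is in section 9.5.4. Its opening question is "Har du sykdomsoppbluss (klar forverring) av din revmatiske sykdom nå" (do you have a flare, a clear worsening, of your rheumatic disease now), with the answers no, yes and uncertain. The next line depends on that answer: "Hvis du svarte «Ja» eller «usikker», hvilken dato startet forverringen" (if yes or uncertain, on what date did the worsening start). The last line is "Omtrent hvor mange dager varte forverringen/har forverringen vart" (about how many days did it last, or has it lasted).

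Section 2.3.4 compares the section 7.2 measures between arms at each time point. It also sets a secondary endpoint: "Comparing the proportions that are scheduled for a visit when a serious disease activity worsening (flare) occurs".

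**The concern.** The two sections describe different quantities. The wording in 7.2.1 takes in flares that are over: the patient has experienced one, it occurred on a date, it lasted some days. The form measures whether a flare is present on the day it is completed. A patient who flared for two weeks and recovered before the form arrives should, reading it literally, answer no. The date and duration fields then stay closed.

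The analysis plan cannot repair this, because a date that was never asked for cannot be recovered. At stake are the between-arm comparison of patient-reported flares and possibly the endpoint on being scheduled for a visit when a flare occurs. The protocol does not name the flare source for that endpoint, but 9.5.4 is the only patient-reported flare item that carries a start date.

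**Working it through.** **Wording, side by side**

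| Element | Section 7.2.1 | Form in 9.5.4 |
|---|---|---|
| Opening question | Has experienced a worsening | Has a flare now (*nå*) |
| Recall window | None stated | Day of completion |
| Date | When the flare occurred | When it started, only after yes or uncertain |
| Duration | Days it lasted | Days it lasted or has lasted, only after yes or uncertain |

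The form is also inconsistent with itself. Its duration line offers the past tense (*varte*) next to the continuing one (*har vart*), so it anticipates ended flares that its opening question excludes. Neighbouring items state their windows: the past week in 9.5.2, 9.5.3 and 9.5.5, and the past six months in 9.5.13.

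**Other routes of capture.** The Schedule of Activities (1.3) marks patient-reported outcomes in the extra-visit column. Section 5.1.1 has the visit arranged within two weeks. Section 7.1.5 says an unscheduled visit includes the regular-visit assessments if possible. A flare that led to a visit can therefore be recorded there, if the item is given and the flare is still present. A flare that resolves between forms without a visit has no such route.

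**Share of flares still present at a scheduled form.** The protocol states no flare rate, duration or count, so there is no figure to reproduce. Assume onset uniform over the reporting interval T, a fixed duration D, completed forms and literal answers. The share is then min(1, D/T), with T = 30.44, 91.31 and 182.63 days.

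| Assumed D | Monthly (remote monitoring) | 3-monthly (patient-initiated) | 6-monthly (usual care; common forms) |
|---|---|---|---|
| 7 days | 7/30.44 = 23% | 7/91.31 = 8% | 7/182.63 = 4% |
| 14 days | 46% | 15% | 8% |
| 28 days | 92% | 31% | 15% |
| 60 days | 100% | 66% | 33% |

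Two results follow. On the half-year forms common to all arms, capture is 4% to 33% over this range. If all forms are used, the arms differ by construction. For any duration up to one month, the ratio of monthly to 6-monthly capture is 182.63/30.44 = 6, at the same true flare rate.

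**Direction of bias in the visit endpoint, if this item supplies the flares.** As an illustration, suppose 50% of flares truly lead to a visit, flares without a visit last 28 days, and forms are 6-monthly.

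- Every visited flare is recorded at its visit, and the others only if present at a form: 0.5/(0.5 + 0.5 × 0.153) = 87%.
- Scheduled forms are the only source, and visited flares last 14 days: 0.5 × 14/(0.5 × 14 + 0.5 × 28) = 33%.
- Scheduled forms are the only source, and durations are equal: 50%.

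Under the first rule with 14-day flares in every arm, the same true 50% appears as 0.5/(0.5 + 0.5 × 0.460) = 69% (remote monitoring), 0.5/(0.5 + 0.5 × 0.153) = 87% (patient-initiated care) and 0.5/(0.5 + 0.5 × 0.077) = 93% (usual care).

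**The case against.** The strongest reply is that this is a small wording gap. Section 7.2.1 only paraphrases the question in English. Some recovered patients will answer yes or uncertain anyway, given the past tense in the duration line. A present-state item also avoids long recall. The visit endpoint uses the phrase serious disease activity worsening and does not cite 9.5.4. Section 2.2.2 offers other criteria, an ASDAS increase above 0.9 or a change of at least 2 on the 0–10 patient global, and the choice may sit in the analysis plan.

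Much of this stands. It limits four stronger readings that a reader might infer:

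- *Flares treated at a visit are lost.* Not supported. Sections 1.3, 5.1.1 and 7.1.5 give those flares an additional route, though only if possible.
- *The visit endpoint is biased against successful scheduling.* Not supported. The direction depends on the data source, which the protocol does not fix, and recording at visits would inflate the proportion.
- *Section 7.2.1 defines a count over the reporting interval.* Not supported. It gives no window and asks for one date and one duration.
- *Nearly all flares are missed.* This depends on duration and form frequency. With monthly forms and 28-day flares, 92% would still be present.

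What the reply does not remove is the mismatch itself, and the missing route for flares that resolve between forms without a visit.

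**Conclusion.** The point holds in this limited form. Sections 7.2.1 and 9.5.4 disagree on the period the flare item covers. Answered as printed, the form does not record flares that have ended by the reporting day, and those that resolve without a visit have no other stated route on this item. For assumed durations of 7 to 60 days, capture is about 4% to 33% on 6-monthly forms, 8% to 66% on 3-monthly forms and 23% to 100% on monthly forms. These figures rest on uniform onset, fixed duration, completed forms and literal answers; the protocol supplies none of them.

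The item therefore cannot support a between-arm comparison of flare occurrence. If it feeds the visit endpoint, that denominator is unreliable in a direction that cannot be stated in advance. The primary endpoint and the sample size do not depend on it. The change is worth making but does not threaten the main conclusion.

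**What to change.** Reconcile sections 7.2.1 and 9.5.4 and state one recall period.

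- On the half-year form, identically in all three arms, add: *Since your last half-year form, have you had a flare (clear worsening)?* Attach the existing start-date and duration fields.
- Keep the question about a flare now as a separate point-prevalence item.
- Use the interval item for flare occurrence. With a single date field it shows which patients had at least one flare; it does not count flares.
- State in section 2.3.4 which record supplies the flares for the visit endpoint.

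The cost is one added question in the digital survey and a short correction to the text, with no extra visits or patients. The downside is some recall error over six months, a period the protocol already uses for medication in 9.5.13.

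If the form can no longer be changed, correct 7.2.1 to say that the item records a flare present on the day of reporting. Then do not present it as flare occurrence or use it as the denominator of the visit endpoint.

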9.5.5 BASDAI

Sykdomsaktivitet (BASDAI)

Spørsmålene nedenfor gjelder hvordan du følte deg den siste uken.

1. Hvordan vil du beskrive den generelle graden av utmattelse/tretthet du har erfart? *

[figure not shown]
2. Hvordan vil du beskrive den generelle graden av smerter i nakke-, rygg og eller hofte i forbindelse med din revmatiske sykdom? *

4. Hvordan vil du beskrive den generelle graden av ubehag du har på eventuelle steder som gjør vondt ved berøring eller trykk? *

3. Hvordan vil du beskrive det generelle nivået av smerte/hevelse du har hatt i ANDRE LEDD enn nakken, ryggen eller hofte? *

5. Hvordan vil du beskrive den generelle graden av stivhet du har opplevd om morgen fra det tidspunktet du våkner? *

[figure not shown]
6. Hvor lenge varer morgenstivheten fra det tidspunktet du våkner? *

9.5.6 BASFI

Angi hvordan du greide følgende aktiviteter den siste uken:.

[figure not shown]
1. Ta på strømper eller strømpebukser uten assistanse eller ved bruk av hjelpemiddel (for eksempel strømpe-påtrekker)?

2. Bøye deg forover fra midjen for å plukke opp en penn fra gulvet uten å bruke et hjelpe middel

3. Nå opp til en høythengende hylle uten bruk av hjelpemedler (for eksempel gripetang).

4. Reise deg fra en spisebordsstol uten armlener eller annen hjelp

5. Beise deg opp fra liggende stilling på gulvet uten hjelp?

6. Stå oppreist uten støtte i 10 min, uten å få ubehag

7. Gå opp 12-15 trappetrinns uten å bruke rekkyverk eller gåstøtte. En fot på hvert trinn.

8. Se deg over skulderen ute på venstre kroppen.

8. Utvärderingskriterium för att identifiera en tillitssituation (baserat på författningskritiken, begrundat allmänt)

For more information, contact the Office of the Secretary of State.

9.5.7 EQ-5D-5L

EQ-5D-5L.

Klikk på den ENE boksen som best beskriver helsen din I DAG.

GANGE *

- Jeg har ingen problemer med å gå omkring
- Jeg har litt problemer med å gå omkring
- Jeg har middels store problemer med å gå omkring
- Jeg har store problemer med å gå omkring
- Jeg er ute av stand til å gå omkring

PERSONLIG STELL *

- Jeg har ingen problemer med å vaske meg eller kle meg
- Jeg har litt problemer med å vaske meg eller kle meg
- Jeg har middels store problemer med å vaske meg eller kle meg
- Jeg har store problemer med å vaske meg eller kle meg
- Jeg er ute av stand til å vaske meg eller kle meg

VANLIGE GJØREMÅL *

(f.eks. arbeid, studier, husarbeid, familie- eller fritidsaktiviteter)

- Jeg har ingen problemer med å utføre mine vanlige gjøremål
- Jeg har litt problemer med å utføre mine vanlige gjøremål
- Jeg har middels store problemer med å utføre mine vanlige gjøremål
- Jeg har store problemer med å utføre mine vanlige gjøremål
- Jeg er ute av stand til å utføre mine vanlige gjøremål

SMERTER / UBEHAG *

[figure not shown]
- Jeg har verken smerter eller ubezag
- Jeg har litt smerter eller ubezag
- Jeg har middels sterke smerter eller ubezag
- Jeg har sterke smerter eller ubezag
- Jeg har svært sterke smerter eller ubezag

ANGST / DEPRESJON *

- Jeg er verken engstelig eller deprimert
- Jeg er litt engstelig eller deprimert
- Jeg er middels engstelig eller deprimert
- Jeg er svært engstelig eller deprimert
- Jeg er ekstremt engstelig eller deprimert

- Vi vil gjerne vite hvor god eller dårlig helsen din er I DAG.
- Denne skalaen er nummerert fra 0 til 100.
- 100 betyr den beste helsen du kan tenke deg.
- 0 betyr den dårligste helsen du kan tenke deg.
- Vennligst klikk på skalaen for å angi hvordan helsen din er I DAG.

Den beste helsen du kan
tenke deg

Den dårligste helsen du
kan tenke deg

[figure not shown]
9.5.8 WPAI item no. 6

Hvor stor innvirkning hadde din revmatiske sykdom på din evne til å utføre vanlige, daglige aktiviteter, utenom arbeid i løpet av de siste 7 dagene? *

Med vanlige aktiviteter mener vi de vanlige aktivitetene du utfører, f.eks. husarbeid, handling, omsorg for barn, trening, studering, osv.

Hvis din revmatiske sykdom innvirket bare litt på dine aktiviteter, velger du et lavt tall. Velg et høyere tall hvis din revmatiske sykdom hadde stor innvirkning på dine aktiviteter.

Tenk kun på hvor stor innvirkning din revmatiske sykdom hadde på din evne til å utføre dine normale daglige aktiviteter, utenom arbeid.

